Rationale for exoskeleton-assisted training of arm and wrist movements: There is evidence that treatment intensity has a profound effect on motor recovery and the use of robotic exoskeleton devices has potential to automate labor-intensive therapy procedures (Backhus et al., 2010; Sanchez et al., 2006). In this context, rehabilitative robotic exoskeleton devices can deliver high-dosage, high-intensity repetitive training of single joint movements or functional tasks by coordinated multi joint movements and can provide immediate feedback about performance. Our research team at NeuroRecovery Research Center at TIRR /Memorial Hermann, demonstrated that robotic exoskeleton- assisted training can provide positive gains in arm and hand functions in neural recovery ([name] et al., 2011; Kadivar et al., 2011). These observations have been supported by others (Zarrifa et al., 2011; Cortes et al., 2013).

3. PURPOSE OF THE STUDY:

The purposes of this project are: a) to evaluate if adults with chronic acquired brain injury can improve their upper-limb voluntary movement by participating in a therapeutic program that combines non-invasive spine stimulation with exoskeleton-assisted training (E-A training) to investigate neuroanatomical and neurophysiological mechanisms of therapeutic improvement. Our preliminary data and the literature support the model that augmentation of activity in spared corticospinal tract (CST) axons is a critical mechanism of motor improvement, and furthermore that CST activity can be increased by repetitive motor training and by electrical stimulation of the cervical spinal cord. Therefore, our project will address the goals of providing a direct, beneficial impact to persons with acquired brain injury while, at the same time, investigating the mechanisms that result in improved function.

4. DESCRIPTION OF STUDY:

Fifteen patients with weakness on one side of the body due to stroke ABI will receive ten sessions combined treatment of 20 minutes of 2.5 mA anodal, cathodal, and sham tsDCS over cervical spine combined with high intensity exoskeleton-assisted arm training, five days a week, for 2 consecutive weeks.

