Baseline Assessment (Visit 2, duration: three to four hours): The baseline assessment can be on the same visit as screening and will be performed in the Motor Recovery Laboratory by an evaluator blinded to subject's group assignment. Subjects will be evaluated for upper extremity motor functions. Primary clinical outcome measure is Fugl-Meyer Assessment (FMA). Secondary clinical outcome measures will be Jebsen Taylor Hand Function Test (JTHFT), box and block test Modified Ashworth Scale (MAS by Bohannon & Smith 1987), Motor Activity Log (MAL), and neurophysiologic testing for spinal conductivity (SSEP), spinal reflexes and exoskeleton measurements for movement quality. Patients who are eligible also will undergo neurophysiological and neuroimaging testing with transcranial magnetic stimulation and one-hour MRI scan.

Neurophysiological testing: Transcranial Magnetic Stimulation (TMS) uses electromagnetic induction to induce weak electric currents using a rapidly changing magnetic field. Single pulse

TMS causes neurons in the cortex under stimulation site to depolarize and discharge an action potential. In the current study we will use single pulse TMS for recording neurophysiological changes of corticospinal tract after treatment in comparison to baseline and at follow-up visits. Single pulse TMS will be applied over corresponding motor cortex and motor threshold (MT) will be determined. Single pulse TMS has been reported as safe. However subjects may experience; headache or neck pain which may occur due to extra muscle tension and from the straight posture of the head and neck during the application of TMS and ringing in the ear and due to loud clicking sound. In order to mitigate the aforementioned side effects, people will be asked to wear earplugs and will be offered acetaminophen or aspirin for pain. Recording motor evoked potentials: In order to record the muscle activity caused by the stimulation of movement related brain tissue, small surface electrodes will be placed on hand and forearm.

Somatosensory evoked potentials (SSEP): to assess the conduction in the somatosensory pathway electrical stimulation will be applied over arm median nerve. Procedure will follow per clinical protocol.

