Exoskeleton-assisted training: The side being trained (right vs left arm) will be weaker side of the body. Treatment will be provided by [name], in a dedicated therapy area in the UTHealth Motor Recovery Lab at TIRR-Memorial Hermann. Subjects will individually perform upper-extremity therapy exercises that are supported by the exoskeleton device. Activities that the subjects will be asked to perform will be selected based on the subject's upper-extremity motor function, including elbow flexion-extension, forearm pronation-supination, wrist flexion-extension, and radial-ulnar deviation. The tasks will be repeated multiple times per session for improved performance. Graphic feedback about performance will be given after each attempt in order to maintain motivation. Rest breaks will be given in order to avoid fatigue.

fNIRS: to measure brain activity over the treatment duration at the beginning of each session fNIRS system will be placed over the head of the subject. Brain activity will be recorded during rest (no active movement with the hand) and during movement (performing a motor task with hand).

Safety Assessment:

Questionnaire: At the end of each therapy session, tsDCS side effects questionnaire will be used to monitor any adverse events and study adherence (attachment 3). At the end of each session, the subject will describe any sensations they felt during stimulation and if they feel anything unexpected happened during the study visit. In addition the subject will be asked to rate his/her level of fatigue, pain, and satisfaction with the activities during the session.

Tolerability Assessment: Participants will be asked to rate the cervical spine unpleasantness and discomfort with a subject scale defining the level from “no discomfort at all” to “unbearable discomfort”.

Post-treatment and Follow-Up Assessment (Visit 13-15, duration: one and a half hours): During this period subjects will be asked to come within a-week after they have completed the study, at week-1 and month-1. Month-1 assessment will serve as the baseline assessment of the next treatment arm. Motor functions tests, exoskeleton measures and neurophysiological measurements with SSEP, TMS and fNIRS will be repeated after the treatment, at 1-week and at 3- months follow-up visits. MRI scan will be performed before and after treatment only.

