Portion of assessment sessions will be videotaped and/or photographed. Subjects will be asked to move or manipulate some objects with the arm while a project staff member will record or photograph. Subjects’ consent will be required to perform and photography or videotaping.

Screening, assessment and treatment sessions will be held at the UTHealth Motor Recovery Laboratory at The Institute for Rehabilitation and Research and at UTHealth Medical School, MRI Facility. A total of up to 42 visits are required. Each visit will take about one-and-a-half hour. Schedule of assessments is shown in Table 1.

Table 1. Schedule of assessments for adults with ABI for the first arm of the design. The subjects will undergo same study schedule in second and third treatment arms (See figure 1).

Assessment	Screening	Baseline Assessment	Intervention period											Post-treatment Assessment	Follow-Up Assessment at 1- week	Follow-Up Assessment at 1- Months		
	Day7- to Day1	Day 1	Day 4(±3) to Day 15(±3)											Day 19(±3)	Day 26 (±4)	Day 45 (±5)		
	Visit 1	Visit 2	Visit 3-12											Visit 13	Visit 14	Visit 15		
ICF	X																	
I/E Criteria	X	X																
Randomization	X																	
Demographics	X	X																
Medical History	X	X																
ASIA (motor and sensory score)		X														X	X	X
Modified Ashworth Scale		X														X	X	X
NHPT		X	X	X	X	X	X	X	X	X	X	X	X	X	X	X	X	X
Motor Activity Log		X	X	X	X	X	X	X	X	X	X	X	X	X	X	X	X	X
Grip Strength		X														X	X	X
Pinch Strength		X														X	X	X
JTHFT		X														X	X	X
FMA		X														X	X	X
Exoskeleton Measurement		X														X	X	X
tsDCS			X	X	X	X	X	X	X	X	X	X	X	X	X			
tsDCS related side effects			X	X	X	X	X	X	X	X	X	X	X	X	X			
MRI Scan		X														X		
TMS		X														X	X	X
SSEP		X														X	X	X
EEG		X														X	X	X
Spinal reflex		X														X	X	X
fNRIS		X	X	X	X	X	X	X	X	X	X	X	X	X	X	X	X	X
Adverse Events		X														X	X	X

[figure not shown]

Figure 1. The cross-over design of the study is illustrated. Abbreviations: Post-tx=Post-treatment assessment, EAAT= Exoskeleton -assisted arm training, tsDCS=transcutaneous spinal direct current stimulation, 1 w f/u= 1 week follow-up after the study intervention, 1 m f/u=1 month follow-up assessment after the study intervention.

Specimens to be collected, including frequency and size/amount: None.

5. SUBJECT POPULATION:

Fifteen adults with acquired brain injury (ABI) will be recruited from TIRR Memorial Hermann,

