Data analysis: Analyses will be performed with two-tailed significance tests at the 95% confidence level and are planned using parametric methods with continuous variables.

However, before performing parametric analyses we will examine the data for evidence of assumption violations and, if such violations are serious, we will perform data transformations or use non-parametric methods as appropriate. Four comparisons will be made. The primary efficacy variable will be the change in hand functions as measured with Jebsen-Taylor Hand Function test. Secondary outcome measures include change in strength of selective muscle groups, change in movement function and number of subjects who will reach minimally clinical significant change (ARAT), and muscle tonus (Modified Ashworth Scale) and change in movement smoothness (exoskeleton measurements), and change in the neurophysiological responses of central nervous system (TMS, SSEP). Adverse effects will be monitored with a Side Effects Questionnaire.

Within subject comparison of after treatment vs. baseline will be performed, separately for each group, using paired t-test. Second, a between groups will examine the effects of treatment by using a repeated measures of ANOVA to test for a time x group interaction. Third subjects' ratings of pain and fatigue after each therapy session will be compared the pain and fatigue ratings, to determine if there was unacceptable to subjects.

The level of significance used will be $p < 0.05$.

Analysis for Neuroimaging scans: Biological correlates of the tsDCS and training will be obtained by computing white matter fiber integrity measures of the CST using diffusion tensor imaging an analysis in AFNI (Cox, 1996) and DTI Query (Sherbondy et al, 2005). Integrity measures will include fiber tract density, strength, and their interaction (Ellmore et al 2011), as well as a comparison of parallel and perpendicular diffusivities to investigate changes in axonal integrity and myelination, respectively. We specifically predict that tsDCS combined with repetitive training will result in increased white matter integrity, including increased fractional anisotropy, increased tract density, and changes in axial and radial diffusivities that are consistent with improved myelination and axonal coherence.

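### Section 4 makes the Fugl-Meyer Assessment primary and Jebsen-Taylor secondary; Section 7 makes change in Jebsen-Taylor primary and does not name Fugl-Meyer

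*Combined protocol and SAP*

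**What the plan says.** **Section 4, Baseline Assessment (Visit 2).** "Primary clinical outcome measure is Fugl-Meyer Assessment (FMA"). The ranking continues in the next sentence: "Secondary clinical outcome measures will be Jebsen Taylor Hand Function Test (JTHFT"), followed by the other secondary measures.

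**Section 7, Data Analysis.** "The primary efficacy variable will be the change in hand functions as measured with Jebsen-Taylor Hand Function test". The secondary list that follows covers muscle strength, movement function with an ARAT responder count, the Modified Ashworth Scale, exoskeleton smoothness, TMS and SSEP. FMA is not named anywhere in Section 7. Testing is two-tailed at p < 0.05. The planned efficacy analyses are a paired t-test of post-treatment against baseline, done separately for each condition, and a repeated-measures ANOVA for a time x group interaction.

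**Section 4, Table 1.** JTHFT and FMA are both scheduled at baseline (Visit 2), post-treatment (Visit 13) and the two follow-ups (Visits 14 and 15). Neither is marked as primary. The legend says of the later periods: "The subjects will undergo same study schedule in second and third treatment arms".

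**Section 3, Purpose.** The aim is "to evaluate if adults with chronic acquired brain injury can improve their upper-limb voluntary movement".

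**The concern.** A primary outcome does its work only if it is fixed before the results are known. Here each of two tests is called primary by one section of the same document. Both are measured on the same participants at the same visits, so at the end of the trial both results will be available, and whichever is reported as primary will agree with one section.

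Two consequences follow. If FMA and JTHFT disagree, the document does not say which gives the trial's answer. If the choice can be made after the data are seen, the chance of a false-positive primary result for a given comparison can exceed the 5% at which each test is run.

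**Working it through.** **Step 1: the statements side by side.**

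| Place | FMA | JTHFT |
|---|---|---|
| Section 4, Baseline Assessment | Primary | Secondary |
| Section 7, Data Analysis | Not named | Primary (change) |
| Table 1 | Visits 2, 13, 14, 15; no rank | Visits 2, 13, 14, 15; no rank |

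Both sections are current text, not an amendment log, and no redaction affects them.

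**Step 2: can other text break the tie?**
- Section 3 speaks of upper-limb voluntary movement in general.
- Section 2 singles out hand dexterity, but under a heading about upper-limb motor function.
- Neither settles which test was intended, and Table 1 ranks neither.

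**Step 3: which analysis and which visits?** The paired test compares post-treatment with baseline. Table 1 has a separate post-treatment assessment at Visit 13, so the natural reading for that test is Visit 13 against baseline. Section 7 does not say which visits enter the time x group ANOVA, or whether the paired test or the ANOVA gives the primary result.

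**Step 4: illustrative size of a free choice.** The documents give no figure to reproduce: there is no sample-size calculation and no correlation between the tests.

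Inputs:
- two tests, each two-sided at 0.05 (Section 7), so the critical value is 1.96;
- correlation r between the two test statistics, which is assumed.

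With both null hypotheses true and (Z1, Z2) bivariate normal with correlation r:

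P(at least one false positive) = 1 - P(|Z1| < 1.96 and |Z2| < 1.96)

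At r = 0 this is 1 - 0.95² = 1 - 0.9025 = 0.0975. For other r the joint probability comes from the bivariate normal distribution:

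| Assumed r | P(neither significant) | P(at least one false positive) |
|---|---|---|
| 0 | 0.9025 | 0.0975 (9.8%) |
| 0.5 | 0.9093 | 0.0907 (9.1%) |
| 0.7 | 0.9165 | 0.0835 (8.3%, unrounded 0.08345) |
| 0.9 | 0.9296 | 0.0704 (7.0%) |

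A simulation of paired t-tests with 15 participants (400,000 trials) gave 0.097, 0.092, 0.085 and 0.072 at the same correlations, so the normal approximation is adequate here.

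**The case against.** **Different labels.** Section 4 says clinical outcome measure and Section 7 says efficacy variable, so the two might be different roles. This fails, because Section 4 explicitly ranks JTHFT as secondary.

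**FMA may be covered in Section 7.** The secondary list is introduced as non-exhaustive and contains an entry for change in movement function, which might cover FMA. This stands in part: a reader should not infer that FMA is certain to go unanalysed. But the entry does not name FMA, sits beside ARAT and is secondary, so the conflict over the primary remains.

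**The time point is not wholly open.** A reader might infer that Section 7 gives no visit at all. The documents do not support that: the paired test compares post-treatment with baseline, which most naturally means Visit 13. The gap is narrower, as set out in Step 3 of the working.

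**The error figures describe a rule nobody wrote.** This is correct. Section 7's 5% is a per-test level, not a trial-wide rate, and the plan also runs paired tests in each of three conditions plus an ANOVA. Naming one outcome would not by itself hold the overall rate at 5%. The figures isolate the FMA/JTHFT choice only.

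**A small trial needs less formality.** With 15 participants the study is modest, but Section 7 still declares one primary efficacy variable and a significance level. Those mean little unless the variable is fixed.

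**Conclusion.** The contradiction is explicit and must be fixed. Two sections of current text name different primary outcomes, one of them ranks the other's primary as secondary, and nothing reconciles them. This conclusion rests on the text alone and needs no numerical assumption.

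The illustrative size is a false-positive chance of 7.0% to 9.8% for one comparison, against 5% per test. It assumes correlations from 0.9 down to 0, true null hypotheses for both tests, and that success on either could count. A reader might infer that the trial's type I error is 9.8%. The documents do not support that, because they contain no either-test rule and the figure leaves out the other planned comparisons. Nor do they show which test the sponsor intended, or that any selective choice has been made.

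Two related defects are separate and are not needed for this conclusion:
- **Last follow-up.** Section 4 (Post-treatment and Follow-Up Assessment) says "Month-1 assessment will serve as the baseline assessment of the next treatment arm", then says that the measurements "will be repeated after the treatment, at 1-week and at 3- months follow-up visits". Table 1 gives 1 month.
- **ARAT.** Section 7 plans the "number of subjects who will reach minimally clinical significant change (ARAT"), but ARAT is not in Section 4's outcome list or Table 1.

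**What to change.** Before unblinding, the sponsor should:

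1. Name one primary outcome, in identical words, in Sections 4 and 7. The choice is the sponsor's, since the documents do not settle it.
2. Give the other test an explicit secondary rank and a planned analysis in Section 7.
3. State whether the paired test or the time x group ANOVA gives the primary result, and which visits enter it. If Visit 13 against baseline is meant for the paired test, say so.

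**Cost.** This is a wording change in two sections, with no new data, visits or patients. One test loses primary status. After unblinding, the choice could no longer be shown to be independent of the results.

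**If two primaries are preferred,** state whether either or both must succeed. An either rule needs an alpha rule, such as 2.5% for each test or Holm. A both rule needs no alpha split. The effect on power of the planned ANOVA cannot be calculated from the documents, which give no SD, effect size or within-subject correlation.

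**Separately,** reconcile the timing of the last follow-up between the Section 4 text and Table 1. Also reconcile ARAT: either list and schedule it, or base the responder count on a test that is already collected, with a pre-stated threshold in both cases.

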The study will use cross-over, randomized, sham controlled, double-blinded design in which 15 participants with subacute or chronic ABI will be assigned to receive either active anodal spinal stimulation, cathodal spinal stimulation, and sham spinal stimulation experiments for the same duration in a random order. In all the experiments participants will receive exoskeleton-assisted training for duration of 1.5 hours. The first 20 minutes of training will be coupled with spinal

stimulation. Treatment will be administered at an intensity of 5 sessions per week for 2 weeks (Please see study HSC-MS-15-0269 PI: [name]).

Pre-screening Procedures: During the pre-screening process, potential subjects with ABI will be contacted by phone from research personnel. The aim and details of the study will be explained in details (reading from a phone script) and information such as demographics, medical history, medications being used, etc. will be gathered. Also ABI subjects will be screened for tsDCS and transcranial magnetic stimulation (TMS) contraindications (attachment 1, attachment 2) and a subgroup of patients (n=5) will be screened for MRI contraindications (attachment 3). The pre-screening will last about 30 minutes and will be performed in a private area. Once this information is collected, the coordinator will consult with the Drs. [name] (PI) and [name] and they will give final approval for the subject to come to The Institute for Rehabilitation and Research Memorial Hermann for the screening procedure.

Screening (Visit 1, duration: One hour): After subject arrives at TIRR a research personnel will meet him/her at the Motor Recovery Laboratory. The details of the study-specific procedures will be reviewed with the subject together. Subject will be screened for inclusion and exclusion criteria. Signed and dated informed consent will be obtained. Demographics, medical history, list of medications will be recorded. If the subject is female in child bearing ages, a urine pregnancy test will be requested. A medication diary will be given to the subject and asked to document all changes in type and dosage of the medication he/she has been using throughout the study. This will allow us to differentiate a potential effect of a change in dosage or type of medication on movement recovery. After subject meets all Inclusion and Exclusion Criteria he/she will be randomly assigned to active, cathodal or sham tsDCS group.

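### Section 7 compares the three arms with a between-groups time-by-group ANOVA that neither links a participant's arms nor includes period, although the trial is a three-period cross-over

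*Combined protocol and SAP*

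**What the plan says.** Section 4 (Description of Study) calls the trial a cross-over. Its 15 participants receive active anodal stimulation, "cathodal spinal stimulation, and sham spinal stimulation experiments for the same duration in a random order". Table 1 gives the schedule for the first arm and says that it is repeated for a second and third. Under Post-treatment and Follow-Up Assessment, "Month-1 assessment will serve as the baseline assessment of the next treatment arm". The training is common to all arms: "In all the experiments participants will receive exoskeleton-assisted training for duration of 1.5 hours".

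Two places use parallel-group language. Under Screening, once eligible, "he/she will be randomly assigned to active, cathodal or sham tsDCS group". In Section 7 (Data Analysis), the treatment comparison is "a between groups will examine the effects of treatment by using a repeated measures of ANOVA to test for a time x group interaction".

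Section 7 also plans this: "Within subject comparison of after treatment vs. baseline will be performed, separately for each group, using paired t-test". It announces four comparisons and describes three: this one, the ANOVA, and one of pain and fatigue ratings. It does not mention period, order, or a participant effect across arms, and it does not say which visits make up time.

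**The concern.** A cross-over gains its precision by comparing treatments inside the same person. An analysis that does not say the three arms come from one person may lose that gain, and its standard error then does not match the design. With 15 participants and no stated power basis, within-person precision is the main statistical reason for the design.

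Period matters because each arm adds ten more sessions of the same exoskeleton training. The gain from training may therefore differ between the first and third blocks. Giving each arm its own baseline deals with a shift in level, but not with a gain that changes from block to block.

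The per-arm paired t-tests do not fill the gap. They pair before with after inside one arm and never compare arms.

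**Working it through.** The plan has no figure to reproduce: 15 is given without an effect size, SD, correlation or power. The check is therefore of design against analysis, followed by an illustration on assumed inputs.

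**1. Three periods per participant?** Table 1 has 1 screening + 1 baseline + 10 sessions + 3 assessments = 15 visits for the first arm. Later arms reuse the month-1 visit as baseline, so each adds 10 + 3 = 13, and 15 + 13 + 13 = 41. Counting 14 per arm (baseline, sessions, assessments) gives 3 x 14 = 42. Section 4 states: "A total of up to 42 visits are required". Either count fits three arms per person; a single arm would need 15 visits.

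**2. Standard error if arms are separate groups.** Assume change-score SD 1, n = 15, and correlation r between one participant's changes in different arms. With no period effect, for a difference between two arms:
- SE used: sqrt(2/15) = 0.365.
- True SE: sqrt(2(1 - r)/15) = 0.258 at r = 0.5, and 0.408 at r = -0.25.
- Ratio of used to true: 1.41 (too wide) and 0.89 (too narrow).

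**3. Standard error if arms are linked but period is left out.** With a period-balanced order, the residual mean square becomes (1 - r) + 15 x S/28, where S is the sum of squared deviations of the period gains from their mean. At r = 0.5:
- Gains 1.0/0.5/0.25: mean 0.583 and S = 0.174 + 0.007 + 0.111 = 0.292. The added term is 0.156, so the residual rises from 0.500 to 0.656 and the SE is multiplied by sqrt(0.656/0.500) = 1.15.
- Gains 0.5/0.25/0.125: S = 0.073, added term 0.039, SE multiplied by 1.04.
- No period effect: no change.

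**4. Power and false positives.** If time means baseline and post-treatment only, the time-by-group F equals the treatment F on change scores, with 2 numerator degrees of freedom. Residual degrees of freedom are 45 - 3 = 42 (separate groups), 14 x 2 = 28 (participant only) and 45 - 15 - 2 - 2 = 26 (participant and period). Further assumptions: 15 complete participants, only anodal works (0.8 SD), no carry-over, and each treatment given to five people in every period. Participant effects are fixed. Each setting has at least 20,000 simulated trials.

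Power at r = 0.5:

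| Training gain by period (SD) | Separate groups | Participant only | Participant + period |
|---|---|---|---|
| None | 56% | 87% | 86% |
| 0.5/0.25/0.125 | 54% | 85% | 86% |
| 1.0/0.5/0.25 | 49% | 77% | 87% |

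The last column does not depend on the period gains; its one-point differences are simulation error.

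- At r = 0 there is little or no gain: 58/56/56% with no period effect and 53/49/56% with gains 1.0/0.5/0.25.
- Rejection of a true null by separate groups, across these trends: 0.3-0.5% at r = 0.5 and 7-9% at r = -0.25. With participant and period it is about 5% throughout.
- At r = -0.25 the participant-plus-period model has power of 46-47%, against 55-59% for separate groups, but the latter is not a valid 5% test there.

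**The case against.** A repeated measures ANOVA in a cross-over is naturally run with arm as a within-participant factor, and Section 7 nowhere says that the arms are independent. This stands in part. A reader might infer that the arms will certainly be analysed as separate groups, and the text does not support that. It does call the comparison a between-groups one, however, and ties the repeated measures to time, so the link is left open. The within-participant reading still has no period term.

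On that second reading the defect may be minor. This stands too: the loss is nil with no period effect and about 1 to 2 power points for the shallow trend. The larger loss needs a steeper trend, which the documents neither give nor rule out.

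Three other inferences go too far:
- That this is the plan's only test of stimulation against sham. Four comparisons are announced and three described, so it is only the one described.
- That the figures above are the power of the planned test. Section 7 does not define time, and Table 1 schedules both the Jebsen-Taylor test and the Fugl-Meyer assessment at four visits per arm. With all four the interaction has 3 x 2 = 6 degrees of freedom and no longer equals the change-score test.
- That the plan offers the paired t-tests as evidence for stimulation. It does not. They fit the aim in Section 3, whether adults with brain injury "can improve their upper-limb voluntary movement by participating in a therapeutic program that combines non-invasive spine stimulation" with training. They cannot credit a gain to stimulation, because every arm includes the training.

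**Conclusion.** The concern holds as a gap in specification that should be fixed. The design is a three-period within-participant cross-over, and the one described comparison of stimulation with sham neither links a participant's arms nor includes period.

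On the separate-groups reading the error bars are wrong in a direction that depends on the sign of the correlation. A reader might take the harm to be lost power alone; that is true only for positive correlation. With negative correlation, which a ceiling on improvement could produce, false positives exceed 5%. On the within-participant reading the harm is lost precision, and only if the training gain differs by period.

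The sizes rest on assumed SD, effect, correlation and period gains, complete data, two visits per arm, balanced order and no carry-over. None of these comes from the documents. The textual finding does not depend on them.

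**What to change.** - **Model.** Replace the time-by-group ANOVA with a cross-over analysis of the change in the primary outcome, from each arm's own baseline to its post-treatment visit, with treatment, period and participant as fixed effects. First settle which outcome is primary: Section 4 (Baseline Assessment) names the Fugl-Meyer assessment and Section 7 the Jebsen-Taylor test. A mixed model is acceptable if its within-participant covariance may be negative. A random participant variance bounded at zero gave null rejection of 8.5-9.2% at correlation -0.25.
- **Reporting.** Test treatment overall at 0.05, and give anodal-sham and cathodal-sham differences with 95% confidence intervals.
- **Paired t-tests.** State that they describe training plus stimulation and do not show a stimulation effect.
- **Allocation.** Reword the Screening paragraph so that participants are randomised to a treatment order, preferably from a period-balanced list. One option uses the three orders of one Latin square twice each and those of the other three times each (6 + 9 = 15).

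The cost is one paragraph and 2 degrees of freedom for period, which is under 1 power point with a balanced list and no period effect. With fixed participant effects, anyone who completes only one period does not contribute to the treatment comparison. If randomisation has started, the model still applies. Multiplicity control of the two contrasts and a period-1-only check for carry-over are optional extras, not part of this error.
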